8.9.2.1 Sensitivity Analysis

The primary analyses (MMRM) for assessing primary efficacy variable are valid if the missing data are missing at random (MAR), meaning that the probability of a value being missing, conditional on the observed data and factors in the statistical model, is random and not dependent on the unknown value of the missing data point. Therefore, two sensitivity analyses under missingness not at random (MNAR) will be conducted for the primary efficacy variable to evaluate the robustness of efficacy results and the effect of missing data.

Sensitivity analysis using a copy-reference multiple-imputation method will be performed to assess the robustness of the primary analysis based on MMRM. In this sensitivity analysis, intermittent missing values will be imputed using the Markov Chain Monte Carlo (MCMC) methodology which assumes a multivariate normal distribution over all variables included in the imputation model. This imputation will be done by treatment group, using MI procedure in SAS 9.4. This imputation will be done by treatment group. Then all the monotone missing values will be multiply-imputed using the imputation model built from the control group, i.e., assuming the missing data in the treatment group will have a profile that equals the profile of the control group for all time points (i.e., a copy-reference imputation). The missing data imputation will be implemented using PROC MI in SAS 9.4 with the MNAR statement. The change from baseline values from each of the completed datasets will then be analyzed using MMRM to include terms for treatment and baseline. The results will be combined using SAS PROC MIANALYZE. It is known that this approach may produce an inflated variance estimate for the treatment comparison. To get a correct variance, a pattern mixture model approximation method will also be used. Results from both the MIANALYZE and the pattern mixture model approximation will be presented as sensitivity analyses.

An additional sensitivity analysis using the tipping-point approach will be conducted. The Variant 3 of the tipping point will be applied ([Ratitch 2013](#)). The technical details for the sensitivity analyses will be provided in the SAP.

8.9.3 *Secondary Endpoints*

Key Secondary

- Change from baseline in awake objective cough frequency after 12 weeks (Day 84) of treatment

- Proportion of subjects with $\geq 30\%$ reduction in 24-hour objective cough frequency per hour at Week 12
- Proportion of subjects with $\geq 30\%$ reduction in awake objective cough frequency per hour at Week 12
- Change from baseline in Cough Severity Visual Analog Scale (VAS) at Week 12

Other Secondary

- Change from baseline in 24-hour objective cough frequency after 4 and 8 weeks (Day 28 and 56) of treatment
- Change from baseline in awake objective cough frequency after 4 and 8 weeks (Day 28 and 56) of treatment
- Change from baseline in 24-hour objective cough frequency at the Follow-Up visit (Day 112)
- Change from baseline in sleep objective cough frequency after 4, 8 and 12 weeks (Day 28, 56 and 84) of treatment
- Change from Baseline in Cough Severity Visual Analog Scale (VAS) at Weeks 4 and 8
- Change from Baseline in Leicester Cough Questionnaire (LCQ) individual Domain and Total scores
- Patient's Global Impression of Change (PGIC)
- Clinician's Global Impression of Change (CGIC)

Statistical approaches for analysis of the secondary endpoints will be detailed in the SAP. The continuous secondary efficacy endpoints will be analyzed using the same MMRM model as used for the primary efficacy analysis.

The categorical secondary efficacy endpoints will be analyzed using the stratified Miettinen and Nurminen (M&N) method, adjusting for gender and country.

Table 2 Analysis Strategy for Primary and Key Secondary Efficacy Endpoints

Endpoint	Statistical Method	Analysis Population	Missing Data Approach
Primary Efficacy Endpoint			
Change from baseline in 24-hour objective cough frequency after 12 weeks (Day 84) of treatment	MMRM	FAS	Observed data only
			Reference-based imputation & Tipping-point approach
Key Secondary Efficacy Endpoints			
Change from baseline in awake objective cough frequency after 12 weeks (Day 84) of treatment	MMRM	FAS	Observed data only
Proportion of participants with $\geq 30\%$ reduction in 24-hour objective cough frequency after 12 weeks (Day 84) of treatment	Stratified Miettinen and Nurminen (M&N)	FAS	Observed data only
Proportion of participants with $\geq 30\%$ reduction in awake objective cough frequency after 12 weeks (Day 84) of treatment	Stratified Miettinen and Nurminen (M&N)	FAS	Observed data only
Change from baseline in VAS after 12 weeks (Day 84) of treatment	MMRM	FAS	Observed data only

MMRM = Mixed Model Repeated Measures; GLMM= Generalized Linear Mixed Model; VAS = Visual Analogue Scales; FAS = Full Analysis set;

8.9.4 *Multiplicity Adjustment*

The study is designed to evaluate the efficacy profile of serlopitant 5 mg versus placebo. The sequential testing procedure will be employed to control the overall Type I error rate at 5% with respect to multiple comparisons for the primary and key secondary endpoints. The procedure will be done in a hierarchical manner. The order of the testing is outlined below.

1. Primary endpoint: serlopitant 5 mg versus placebo
2. Key secondary endpoint #1: serlopitant 5 mg versus placebo
3. Key secondary endpoint #2: serlopitant 5 mg versus placebo
4. Key secondary endpoint #3: serlopitant 5 mg versus placebo
5. Key secondary endpoint #4: serlopitant 5 mg versus placebo

First, the test ranked as first will be tested and the difference will be declared statistically significant if the one-sided p value is less than 0.05. Second, in case that the difference for the first comparison is statistically significant, the comparison ranked as second will be tested, and the difference will be declared statistically significant if the one-sided p-value is less than 0.05. The testing will continue as long as the previously ranked objective was statistically significant.

All other efficacy variables will be tested at the 0.05 level of significance without multiplicity adjustment.

8.10 **Safety Analyses**

8.10.1 *Adverse Events*

The incidence of all AEs and treatment-related AEs will be tabulated by treatment received. These AEs will be classified by system organ class and preferred term using the Medical Dictionary for Regulatory Activities (MedDRA). For incidence reporting, if a subject reported more than one AE that was coded to the same system organ class or preferred term, the subject will be counted only once for that specific system organ class or preferred term. An overview of AEs, which includes subject incidence of AEs, treatment-related AEs, AEs by severity, SAEs, deaths, and AEs leading to discontinuation, will be presented.

SAEs will be listed and summarized in a similar manner to AEs.

8.10.2 *Clinical Safety Laboratory Results*

Clinical safety laboratory values will be measured by a central laboratory. Summary statistics for actual values and for changes from baseline will be tabulated for laboratory results by scheduled visit. Graphs of laboratory values over time will also be produced.

Subjects with clinical laboratory values outside of the normal reference range at any post-baseline assessment will be summarized. Shifts from baseline laboratory values will be tabulated.

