6.5.9 Day 85/Early Treatment Discontinuation Visit

The following procedures and evaluations will be performed at the clinic on Day 85 or within 7 days of the last dose of study drug for subjects who discontinue study drug treatment early.

At this visit, the following procedures and assessments are to be performed:

- Cough severity VAS
- PGIC
- LCQ
- Vital signs
- Weight
- Collect Day 84 cough monitor
- Complete physical exam
- ECG (12 lead)
- Laboratory tests
 - Reproductive endocrine labs for females under 55 years of age at time of consent
 - Endocrine
 - Hematology
 - Chemistry
 - Urinalysis
 - Urine pregnancy test for females of childbearing potential
 - Urine drug screen
- Contact IWRS to register Day 85 end of treatment visit
- Review IVRS/IWRS Days 57–84 dosing diary entries
- The following will be completed by the Investigator (MD or DO):

- CGIC
- Study drug - collect/performance accountability for Days 57–84 bottles (**early treatment discontinuation visit only**)
- Record all AEs
- Record all concomitant medication use
- Schedule Day 112 visit at clinic or at subject's home
- Schedule Day 113 visit at clinic

6.5.10 *Day 112 Follow-up Visit*

Subjects will return to the clinic or be visited by a mobile research nurse on Day 112 (± 3 days) for the following procedures and evaluations:

- Cough severity VAS
- Record all AEs
- Record all concomitant medication use
- Attach and activate cough monitor
 - Cough monitor will be collected the following day by a courier service and delivered to the clinic
- Contact IWRS to register the Day 112 Follow-up visit
- Remind subject about Day 113 visit at clinic

6.5.11 *Day 113 Follow-up Visit*

Subjects will return to the clinic on Day 113 for the following procedures and evaluations:

- Vital signs
- Collect Day 112 cough monitor
- Cough severity VAS
- LCQ
- Contact IWRS to register the Day 113 Follow-up visit
- Complete physical exam
- ECG (12-lead)

- Laboratory tests
 - Reproductive endocrine labs for females under 55 years of age at time of consent
 - Endocrine
 - Hematology
 - Chemistry
 - Urinalysis
 - Urine pregnancy test for females of childbearing potential
 - Urine drug screen
- Record all AEs
- Record all concomitant medication use

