8.1 Decision Rule and Sample Size

The comparisons related to the primary and key secondary endpoints will be done in a hierarchical manner to control the familywise error rate. The testing procedure will start by testing the primary endpoint and then proceed to the key secondary endpoints by following the order as specified in [Section 8.9.4](#).

A total of 170 subjects (85/arm) in 1:1 ratio to serlopitant 5 mg or placebo will provide 90% power to detect a 25% relative reduction (placebo-adjusted ratio of 0.75) in 24-hour objective cough frequency or awake objective cough frequency using a two-sample t-test at a one-sided significance level of 0.05. This assumes that 24-hour cough frequency or awake cough frequency follows a log-normal distribution with a CV of 0.64. This sample size also considers an expected dropout rate of 15%.

The sample size calculations have been performed in nQuery Advisor + nTerim.

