As the change in 24-hour cough frequency may have a skewed and wide distribution, the primary analysis for the primary endpoint will be on the natural log scale of the cough frequency data. The difference between serlopitant 5 mg and placebo will be estimated using a mixed effect repeated measures (MMRM) model. The model will include factors for treatment, visit, country, sex, the treatment-by-visit interaction; and the log-transformed baseline value as a covariate. The MMRM model will use all available 24-hour cough frequency data on Day 28, 56, and 84. An unstructured covariance structure will be applied for MMRM. In case the model will not converge with the unstructured covariance structure, the heterogeneous compound symmetry (CSH) will be used instead. Contrasts will be constructed to compare the serlopitant 5 mg group to the placebo group at each visit. The least-squares (LS) mean change from baseline (on the log scale) with the associated standard errors will be displayed for each treatment group. Estimated treatment differences (serlopitant vs. placebo) along with corresponding CIs will also be presented.

In addition, the geometric mean of 24-hour cough frequency will be presented by treatment and by visit. The percent difference change between serlopitant and placebo will be estimated

by $100(e^{\text{diff}} - 1)$, where diff is the difference provided by the analysis of the log-transformed variable.

An observation of zero coughs per hour will be replaced by a cough rate of 0.1/hr for the calculation of geometric means. If this rule is used the table will have a footnote detailing the participant and treatment. Further details of the model specification, assumptions, and SAS implementation codes will be provided in the SAP.

Furthermore, the changes from baseline in 24-hour cough frequency on the original scale will be also analyzed using a the same MMRM model.

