**Table 2: Analysis Windows**

Analysis Visit	Range	Target Day
Baseline	Day $\leq$ 1	Day 1
Day 28 (Week 4)	Day 2 to Day 42	Day 28
Day 56 (Week 8)	Day 43 to Day 70	Day 56
Day 84 (Week 12)	Day 71 to min (Day 91, TRTEDT+7)	Day 84
Day 112 (Follow-Up)	> min (Day 91, TRTEDT+7)	Day 112

+TRTEDT – date of last study medication

The Follow-Up assessment will be the last assessment available that is at least seven days after the end of treatment. Should no post treatment assessments be available the subject will not have a follow-up assessment. Any assessments reported after the date of last study medication will be considered as a follow-up assessment.

For other efficacy and safety endpoints, the study visits as specified in the protocol will be utilized as analysis visits.

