### **9.6.3.3 Cough Visual Analog Scale**

Cough Visual Analogue Scale (VAS) scored from 0 to 100 using a 100 mm visual analogue scale will be evaluated at Screening, Baseline (Study Day -1), Days 28, 56, 84, Day 85/ETD, Follow-up (Day 112 and Day 113). Baseline cough VAS is defined as the cough VAS at Baseline (Study Day -1).

Change from baseline of cough VAS score will be analyzed in the same way as that for the primary endpoint as indicated in Section 9.6.2.1 above. To explore the correlation between VAS and 24-hour cough frequency, Scatter plots between VAS and 24-hour objective cough frequency counting will be generated.

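### A VAS score taken at the early-discontinuation visit has no place in the H5 model, and the VAS has no missing-data sensitivity analysis: a cheap improvement

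*Protocol*

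**What the plan says.** H5, the last test in the hierarchy of SAP 8.7, is the change in VAS at Day 84.

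- **Model.** Protocol 8.9.3: "The continuous secondary efficacy endpoints will be analyzed using the same MMRM model as used for the primary efficacy analysis". SAP 9.6.3.3: "Change from baseline of cough VAS score will be analyzed in the same way as that for the primary endpoint". For the primary endpoint, Protocol 8.9.2 and SAP 9.6.2.1 say: "The MMRM model will use all available 24-hour cough frequency data on Day 28, 56, and 84". The sample code in SAP Appendix A has those three days as its only visit levels.
- **Collection.** The VAS is scored at Days 28, 56 and 84, and again at the Day 85/ETD visit. Protocol 6.5.9 sets that visit at Day 85 or "within 7 days of the last dose of study drug for subjects who discontinue study drug treatment early".
- **Visit assignment.** SAP 7.3 introduces the Table 2 day ranges for cough frequency. For the rest: "For other efficacy and safety endpoints, the study visits as specified in the protocol will be utilized as analysis visits". The visit map in SAP Appendix C numbers Day 84 as visit 7 and Day 85/ETD as visit 8.
- **Missing data.** Protocol 8.2 and Table 2 analyse the VAS on observed data only. SAP 8.3 and 9.6.5 confine the two missing-not-at-random analyses to 24-hour and awake cough frequency.

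**The concern.** Taking over the primary model costs cough frequency nothing at the ETD visit, because no recording is started there. The VAS differs: a score is collected close to the decision to stop, and the plan gives it no analysis visit.

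Protocol 8.9.2.1 itself says the MMRM is valid when missingness, given the observed data, does not depend on the unseen value. If subjects stop because their cough is bad that week, the ETD score carries that information. Leaving it out makes the assumption harder to meet. Suppose placebo subjects stop for poor control and serlopitant subjects for unrelated reasons. The placebo mean at Day 84 then looks too good and the VAS effect is understated; the reverse pattern overstates it. No sensitivity analysis would show either. Under SAP 8.1, anything not described before database lock is post hoc, so a rule added later would not have confirmatory standing.

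**Working it through.** **1. The plan's own figure.** Protocol 8.1 gives a "two-sample t-test at a one-sided significance level of 0.05", a design that "will provide 90% power to detect a 25% relative reduction (placebo-adjusted ratio of 0.75"), and an endpoint that "follows a log-normal distribution with a CV of 0.64", with 15% drop-out.
- Log-scale SD = sqrt(ln(1 + 0.64²)) = 0.5859; difference = |ln 0.75| = 0.2877.
- n per arm = 2 × (1.645 + 1.282)² × (0.5859/0.2877)² ≈ 71.1, rounded up to 72. The t-test power at 72 is 90.1%.
- 72/0.85 = 84.7, rounded up to 85 per arm, 170 in total. The stated size reproduces.
- Expected drop-outs: 0.15 × 170 = 25.5, about 26. This is an upper limit on the ETD VAS scores at stake. The plan gives no VAS SD, effect, correlation or power.

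**2. Where an ETD VAS can go.** It is visit 8 in the map. The nominal-visit rule leaves it there, the model has no level for it, and no other sentence moves it.

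**3. How many scores the Table 2 ranges could reach.** The ranges are Days 2–42, 43–70 and 71 onward. Assume stopping is spread evenly over 84 days, everyone attends the ETD visit, and a scheduled score in the range takes precedence.

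| Day of ETD visit | Scores of 26 | Outcome |
|---|---|---|
| 1–27 | 26 × 27/84 = 8.4 | No post-baseline cough recording, so outside the FAS |
| 29–42, 57–70 | 26 × 28/84 = 8.7 | Range already holds the Day 28 or Day 56 score |
| 43–55, 71–83 | 26 × 26/84 = 8.0 | Newly usable |
| 28, 56, 84 | 26 × 3/84 = 0.9 | Scheduled days |

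**4. Size of the effect; all inputs assumed.** 85 per arm, SD 25 mm, visit correlation 0.5–0.7, about 15% drop-out. Drop-out before each visit is a logistic function of the current VAS. Day 84 is estimated by sequential regression, which stands in for the MMRM.

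(a) Full-data estimate against the three-visit model. True difference -10 mm, log-odds slope 1.5 per SD in one arm only, 600 runs per row:

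| Correlation | Arm with VAS-driven drop-out | Full data | Without ETD | Shift | All FAS ETD scores used |
|---|---|---|---|---|---|
| 0.5 | placebo | -9.71 | -7.80 | +1.91 | -9.25 |
| 0.5 | serlopitant | -9.96 | -11.40 | -1.44 | -10.41 |
| 0.7 | placebo | -10.10 | -8.70 | +1.40 | -9.69 |
| 0.7 | serlopitant | -10.14 | -11.04 | -0.90 | -10.47 |

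With a true difference of zero, the one-arm shifts are 1.3 to 2.0 mm. With random drop-out, or a slope of 1 in both arms, the largest shift in any setting is 0.33 mm (-10.09 to -9.76). Precision hardly changes (for example, SD of the estimate 3.64 against 3.56).

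(b) The day-range rule as it would operate, with half of the post-Day-28 ETD scores usable. True difference -10 mm, VAS-driven drop-out in the placebo arm only, power at one-sided 0.05:

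| Slope | Plan | All FAS ETD scores | Day-range rule |
|---|---|---|---|
| 1 | -8.2 to -8.3 mm, 64–69% | -9.1 to -9.4 mm, about 75% | -8.7 to -8.8 mm, 70–73% |
| 0.5 | -9.0 to -9.2 mm | – | gain of 0.2–0.3 mm, 2–3 points |

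A separate run at one-arm VAS-driven drop-out gave -7.8 to -8.0 mm under the plan and -8.4 mm with the rule. Taking mid-range values, the share of bias removed is 0.5/1.75 = 29% at slope 1 and 0.5/2.1 = 24% in the separate run.

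**The case against.** An MMRM on scheduled visits is a standard choice and is valid under missing at random given earlier scores. H5 is tested only if H1 to H4 all succeed. The bias needs drop-out driven by current VAS in one arm and not the other, which the documents neither state nor imply. The simulations also flatter any remedy: they treat the ETD score as equal to the missing scheduled score, whereas a real one may come after dosing has stopped and off the target day. All of this stands, and it limits the weight of the point.

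A reader might infer that the plan throws away the exit VAS of every early discontinuer. The documents do not support that.
- Protocol 6.6 allows loss to follow-up and withdrawal of consent, which may leave no ETD score.
- Subjects who stop before the first on-treatment recording are lost through the FAS definition (SAP 6.1), not through visit assignment.
- No sentence excludes the ETD VAS. The sentence naming the three days concerns cough frequency data. That the score is unused follows from reading the rules together.

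A reader might also infer that the plan already accepts scores up to seven days after the last dose. Table 2 does so in its Day 84 row, but the text beneath it classes any assessment after the last medication date as follow-up. The section contradicts itself and cannot be borrowed without comment.

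**Conclusion.** The point holds as a gap in specification with a modest, conditional effect: a cheap improvement, not a flaw that undermines H5. Read together, the nominal-visit rule and the three-visit model leave the ETD VAS out of H5, with no VAS sensitivity analysis behind it.

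The effect is negligible if drop-out is random or equally related to VAS in both arms. If it is driven by current VAS in one arm only, the bias is about 1 to 2 mm against an assumed difference of -10 mm, in either direction. Assigning scores by day range would remove roughly a quarter to a third of that: about 0.2 to 0.6 mm and, where the plan understates the effect, 2 to 6 power points. Full recovery should not be expected, since it would need all dosed subjects in the model, which is a change of analysis set.

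These sizes rest on the assumed SD, correlation, drop-out mechanism and even spread of stopping times. None of these is in the documents except the 15% drop-out rate.

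**What to change.** Before unblinding, add to SAP 7.3 and 9.6.3.3:

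- An ETD VAS taken no later than seven days after the last dose goes to the Day 28, 56 or 84 analysis visit whose Table 2 range contains its actual study day, if the subject has no scheduled VAS in that range. It is never moved automatically to Day 84.
- For completers, the Day 84 score, not the Day 85 score, is the Week 12 VAS.
- The seven-day limit applies to the VAS despite the sentence in 7.3 that treats anything after the last dose as follow-up; alternatively, reconcile that sentence with Table 2.

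If the sponsor prefers to keep H5 on scheduled visits only, it should say so and prespecify the rule above as a VAS sensitivity analysis.

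The cost is a few sentences and some programming, with no new data and no change for completers. The downside is that a few scores may be up to seven days after the last dose and up to about two weeks from the target day.

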8.10.3 Vital Signs

The observed data and change from baseline for each measurement day will be summarized with descriptive statistics.

8.10.4 Electrocardiograms

The overall ECG assessment (abnormal or normal) will be summarized along with a summary of how many subjects developed a post treatment abnormal result. The study relevance of the finding will be provided in a listing.

8.11 Pharmacokinetics Analysis

The PK data and analysis for serlopitant and metabolites will be reported in a PK report that will be a part of the clinical study report.

9 ADMINISTRATIVE ASPECTS

9.1 Changes to the Protocol

Protocol amendments must be made only with the prior written approval of the Sponsor. An investigator signature will be obtained for the initial protocol and any amendments. Substantial amendments will be provided to the appropriate regulatory authorities. No protocol changes affecting the following will be made without the written approval of the Sponsor and the responsible IRB or EC:

- Safety and/or eligibility of subjects
- Data integrity
- Study design or conduct
- Willingness of a subject to participate in the study

